4.3.4 Additional exploratory analyses

In a similar study conducted by the Sponsor, differences in clinical conditions were also identified between centres (ie, room temperature in a specific centre higher than required by the study protocol). Consequently, the centre effect will be investigated and some covariates (ie, room temperature ...) could be included in the statistical models.

Additionally, the following comparisons will be investigated on ITT population only:

- The comparison in TEWL between Day 1 and Week 16 will be performed by skin group (lesional and non-lesional skin area only), STS and spot using a non-parametric Wilcoxon signed-rank test.
- The comparison in TEWL AUC between Day 1 and Week 16 will be performed by skin group (lesional and non-lesional skin area only) and spot using a non-parametric Wilcoxon signed-rank test.
- The comparison between AD participants (lesional skin area/non-lesional skin area) and Healthy participants will be performed on TEWL data at Week 16 using a non-parametric Wilcoxon signed-rank test.
- The comparison AD participants (lesional skin area/non-lesional skin area) versus Healthy participants will be performed on TEWL AUC data at Week 16 using a non-parametric Wilcoxon signed-rank test.

4.3.5 Analyses of safety parameters

All the safety analyses will be performed using the safety population. When applicable, results will be by cohort and overall.

The safety analysis will be conducted according to the Sponsor's document "Analysis and reporting of safety data from Clinical Trials through the Clinical Study Report" (BTD-009536 Version 3.0 dated on 24 May 2014).

4.3.5.1 Adverse events

Adverse events will be coded to a lower level term (LLT), PT, HLT, high level group term (HLGT) and primary SOC using the version of MedDRA in effect at Sanofi at the time of each database lock.

For patients' cohort, they will be classified into predefined standard categories according to chronological criteria:

- Pre-treatment AEs: AEs that occurred, worsened or became serious during the pre-treatment period defined as the time between informed consent signature and the first IMP administration.
- Treatment emergent AEs (TEAEs): AEs that occurred, worsened or became serious during the TEAE period defined as the time from the first IMP administration up to the EoT visit (EoT included).
- Post-TEAEs: AEs that occurred, worsened or became serious during the post-TEAE period defined as the time starting after the TEAE period (including the follow-up period).

Treatment-emergent AEs will be assigned to the treatment received at the time of the AE onset. If the onset date (or time) of an AE (occurrence, worsening or becoming serious) is incomplete or missing, then the AE will be considered as a TEAE unless a partial date (or time) shows it as a pre- or post-treatment event.

For all healthy volunteers, safety data will be considered as part of a single period starting with the signature of the informed consent and ending with the EoS visit (EoS included).

All AEs reported in the study will be listed, sorted by participant, onset date and time.

The following TEAEs summaries will be provided for the patients' cohort of the safety population:

- Overview of TEAEs: number and percentage of participants with any TEAE, any serious TEAE, any TEAE leading to death (if any occurred), any TEAE leading to permanent treatment discontinuation, and any TEAE of special interest.
- Summary of TEAEs by primary SOC and PT:
 - Number and percentage of patients with at least one TEAE.
 - Number of occurrences of TEAEs.

Patients presenting TEAEs will be listed sorted by primary SOC and PT. By definition, no TEAEs summary will be displayed for healthy volunteers. AEs that occur outside the treatment-emergent period or in healthy volunteers will be summarized separately.

In addition, the following listings/summary will be provided:

- Listing of any deaths and serious AEs.
- Listing of any AEs leading to permanent treatment discontinuation.
- Number (%) of patients experiencing treatment emergent adverse events of special interest (AESI) will be presented by AESI category and PT, sorted by decreasing incidence of PT within each AESI category.
- Listing of AESIs.
- Number (%) of patients experiencing at least one treatment emergent COVID19 related adverse event by primary SOC and PT.

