1.1 STUDY DESIGN

Study design

This is a Phase 4 open-label, exploratory study in three sites evaluating the effect of dupilumab on skin barrier function (as measured by transepidermal water loss (TEWL) before and after skin tape stripping [STS]) in pediatric patients aged between ≥ 6 and <12 years old with moderate-to-severe atopic dermatitis (AD) with a healthy volunteer cohort as a reference comparator. Patients with moderate-to-severe AD will be included in the US site and patients with severe AD will be included in the EU site (UK). One more US site was initiated because the recruitment at the first US site was insufficient.

Sample size

Approximately 24 pediatric patients with moderate-to-severe AD will be enrolled. An approximately equal number of age, gender, location of targeted lesion area and site matched healthy volunteers serving as a reference comparator cohort will also be enrolled.

Randomization

Not applicable.

Treatment received

Study participants will be assigned to study intervention as described below:

- Up to 24 pediatric patients with moderate-to-severe AD will receive dupilumab.
- Dose regimen 1: children with baseline $15 \text{ kg} \leq \text{body weight} < 30 \text{ kg}$ will receive a subcutaneous (SC) loading dose of dupilumab 600 mg (2 injections of dupilumab 300 mg) on Day 1 (Week 0), followed by every 4-week SC dosing of dupilumab 300 mg from Week 4 to Week 12.
- Dose regimen 2: children with baseline $30 \text{ kg} \leq \text{body weight} < 60 \text{ kg}$ will receive a SC loading dose of dupilumab 400 mg (2 injections of dupilumab 200 mg) on Day 1 (Week 0), followed by bi-weekly SC dosing of dupilumab 200 mg from Week 2 to Week 14.

The treatment will be given to the pediatric patient (≥ 6 and < 12 years of age) depending on its body weight.

Duration of study period

This is a 32-week study with a 4-week screening period, 16-week treatment phase designed to investigate dupilumab's effect on skin barrier function in approximately 20 pediatric patients with moderate-to-severe AD, and a 12-week follow-up period.

The graphical study design is detailed in [Section 8 \(Appendix A\)](#).

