1.4 STUDY PLAN

The study will comprise of:

- Screening period: Up to 4 weeks (Day -28 to Day -1) from signing the informed consent.
- Baseline visit (Week 0, Day 1): Participants who remain eligible will be enrolled.
- A 16-week open-label treatment phase for AD patients and a 16-week observation period for healthy volunteers.
- Follow-up period for 12 weeks after the end of treatment (EoT) visit (Week 16). Dupilumab may be used as a rescue therapy for AD patients, if needed during follow-up period.

Schedule of activities in pediatric patients and healthy volunteers are detailed in [Section 8](#) ([Appendix B](#) and [Appendix C](#)).

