4.3.2.4 Extent of study treatment exposure and compliance

The extent of study treatment exposure and compliance will be assessed and summarized for patients' cohort within the safety population.

A listing of patients receiving IMP from specified batch (patient, IMP, and IMP batch number) will be performed by patient.

Extent of IMP exposure

Duration of IMP exposure is defined regardless of unplanned intermittent discontinuations as:

- Dose regimen 1: the last dose date - first dose date +28 days.
- Dose regimen 2: the last dose date - first dose date +14 days.

If the patient's date of last dose is unknown, his/her last IMP dispensing date will be used in its place.

Duration of exposure will be summarized in patients' cohort using descriptive statistics as quantitative and qualitative variables (1 day / 2 to 15 days / 16 to 29 days / 30 to 43 days / 44 to 57 days / 58 to 71 days / 72 to 85 days / 86 to 99 days / 100 to 113 days / 114 to 155 days / 156 to 197 days). This description could be performed by trial impact (disruption) due to COVID19 (without and with).

Compliance

A given administration will be considered noncompliant if the patient did not take the planned dose of treatment as required by the protocol. No imputation will be made for patients with missing or incomplete data.

Percentage of compliance for a patient will be defined as the number of administrations the patient was compliant divided by the total number of administrations the patient was planned to take (the number of doses missed due to interruptions at Investigators' judgment will not be subtracted) on or before the last IMP administration date.

Treatment compliance, above-planned and under-planned dosing percentages will be summarized descriptively. The percentage of patients with compliance <80% will be summarized. In addition, number and percentage of patients with at least 1 above-planned dosing administration will be

given, as well as the number and percentage of patients with 0,]0, 20%], and >20% under planned dosing administrations.

4.3.2.5 *Prior/Concomitant medication/therapy*

All medications taken during the study will be coded using the version of world health organization drug dictionary (WHO-DD) in effect at Sanofi at the time of each database lock.

Medications will be classified into three categories, prior, concomitant and post-treatment medications, according to the following rules:

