4.3.5.2 Vital signs

Heart rate, systolic and diastolic blood pressures (SBP and DBP), body temperature and respiratory rate will be analyzed as raw parameter value and change from baseline.

Body weight will be analyzed as raw parameter value and percent change from baseline. BMI will be analyzed as raw parameter value.

Baseline definition

The values to be used as baseline will be the Day 1 (Visit 2, Week 0) predose assessment. If any of the scheduled baseline tests are repeated for any participant, the last rechecked values will be considered as baseline, provided, for patients, they were done before the IMP administration of the respective treatment phase, and in the same condition.

Abnormalities analyses

For vital sign parameters, analysis will be performed using all post-baseline assessments done during the TEAE period/safety period, including all unplanned and rechecked values. Counts of participants with potentially clinically significant abnormal (PCSA) values will be presented by cohort, regardless of the baseline status. PCSA values are defined as abnormal values considered medically important by the Sponsor according to predefined criteria/thresholds based on literature review and defined by the Sponsor.

A listing of individual data from participants with post-baseline PCSAs will be provided; values will be flagged when reaching the PCSA criteria.

PCSA criteria are detailed in [Section 8 \(Appendix D\)](#).

Descriptive statistics and plots

For heart rate, blood pressures, body temperature and respiratory rate, raw data and absolute changes from baseline will be summarized in descriptive statistics for patients' cohort and scheduled time of measurement.

For body weight, raw data and percent change from baseline will be summarized in descriptive statistics by cohort and scheduled time of measurement.

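### Adverse events starting after rescue dupilumab in follow-up are classed as post-TEAE and pooled with events in undosed children, so on-drug incidence in follow-up cannot be read

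*SAP*

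**What the plan says.** All references are to the clinical SAP.

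- **TEAE period (4.3.5.1).** For patients it is "the time from the first IMP administration up to the EoT visit (EoT included". The post-TEAE period is "the time starting after the TEAE period (including the follow-up period". No rule reopens the first period if dupilumab is given again.
- **Follow-up (1.4).** "Follow-up period for 12 weeks after the end of treatment (EoT) visit (Week 16" is planned, and "Dupilumab may be used as a rescue therapy for AD patients, if needed during follow-up period".
- **What the TEAE period governs.** It governs the TEAE overview, the table by organ class and preferred term, and the AESI incidence table (4.3.5.1). For abnormal vital signs, "analysis will be performed using all post-baseline assessments done during the TEAE period/safety period" (4.3.5.2). The single safety period running to the end of study is defined only for healthy volunteers.
- **What it does not govern.** All adverse events are listed, AESIs and serious events have listings not limited to TEAEs, and events outside the TEAE period get a separate summary (4.3.5.1). Descriptive vital-sign statistics are by scheduled time (4.3.5.2).
- **Exposure (4.3.2.4).** Duration is last dose date minus first dose date, plus 28 days (regimen 1) or 14 days (regimen 2). The last dose is not limited to the treatment phase. The top categories are "114 to 155 days / 156 to 197 days".
- **Concomitant medication (4.3.2.5).** The window runs to the last study-drug dose plus the same 28 or 14 days.

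**The concern.** The safety tables fix the end of the on-treatment period to a visit, while the exposure and medication rules follow the last dose. The two agree as long as nobody is dosed after Week 16. Once a child receives dupilumab in follow-up they can part, and the SAP has no rule for that case.

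An AESI starting days after a follow-up dose would then be counted with events in children who have had no dupilumab since the treatment phase. A reader of the report could learn from the listings that the event occurred, but no table would give the frequency of events under follow-up dupilumab. The efficacy sections do allow for rescue in follow-up: change is measured from Week 16 or from the last visit before rescue (4.3.3.2, 4.3.3.3). The safety sections have no counterpart.

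**Working it through.** **Inputs.** First dose on D1. Regimen 1: "every 4-week SC dosing of dupilumab 300 mg from Week 4 to Week 12", so the last scheduled dose is D85 ±3. Regimen 2: "bi-weekly SC dosing of dupilumab 200 mg from Week 2 to Week 14", so the last scheduled dose is D99 ±3 (1.1 and Appendix B). EoT is D113 ±3 and end of study is D197 ±3 (Appendix B).

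**Step 1: scheduled dosing.** Exposure = last dose − first dose + 28 or 14.

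- Regimen 1: (85 − 1) + 28 = 112 days; with a last dose at +3 days, 115.
- Regimen 2: (99 − 1) + 14 = 112 days; with a last dose at +3 days, 115.
- The concomitant-medication window ends on D85 + 28 = D113, or D99 + 14 = D113.

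For planned treatment, then, that window and the TEAE period both end at the nominal EoT day.

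**Step 2: what the upper exposure categories require.** Last-dose day = duration − 28 (or 14) + 1.

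| Category | Regimen 1 last dose | Regimen 2 last dose |
|---|---|---|
| 114–155 days | D87 to D128 | D101 to D142 |
| 156–197 days | D129 to D170 | D143 to D184 |

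The lower category can be entered at its edge (114 or 115 days) by a scheduled dose given late within its visit window. The upper one cannot be reached without a dose after EoT, which is D116 at the latest.

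**Step 3: one follow-up dose, taken on D155 as an example.**

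| End of window | Regimen 1 | Regimen 2 |
|---|---|---|
| TEAE period | D113 | D113 |
| Exposure, if the dose counts as study drug | 154 + 28 = 182 days | 154 + 14 = 168 days |
| Concomitant medication, same condition | 155 + 28 = D183 | 155 + 14 = D169 |

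The 28 or 14 days after this dose lie wholly in the post-TEAE period. That is 28/84 = 33% or 14/84 = 17% of follow-up.

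**Step 4: upper bound per child.** Follow-up is 197 − 113 = 84 days out of 197 − 1 = 196, so 84/196 = 43%. This would need dosing that covers all of follow-up.

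**Step 5: abnormal vital signs.** Body weight is measured at Week 28 (Appendix B), and a loss of at least 5% is a PCSA criterion (Appendix D). If the period for patients is the TEAE period, a child on follow-up dupilumab who meets the criterion at Week 28 is not counted. A healthy volunteer who meets it is counted.

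**The case against.** The case for leaving the text alone has several parts.

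- **Rescue dupilumab may not be study drug.** A reader might infer from the exposure categories that follow-up dupilumab is counted as exposure. The SAP states no such rule. The category limits copy the visit days, and they include a 1-day category that cannot occur, since one dose already counts as 28 or 14 days. A dose on D197 would give 224 or 210 days, beyond the last category. The limits look like a visit grid, so they do not prove intent. This stands. What remains is that the SAP never settles the question: if follow-up dupilumab is study drug, the windows conflict; if it is not, the 156–197 day category cannot be filled.
- **Nothing is lost.** It is tempting to say that these events vanish from the report. They do not: they are listed and summarised outside the TEAE tables. This also stands, but the separate summary does not distinguish dosed from undosed children.
- **Not all vital-sign output is affected.** Correct. Only the PCSA counts use the TEAE period, and even there the wording is loose.
- **No rate is understated against exposure.** Correct. The SAP reports numbers and percentages of patients, not exposure-adjusted rates.
- **A fixed window suits the design.** The Week 16 analysis contains TEAE summaries only (section 6), and a period ending at EoT keeps those tables stable. Extending it to the later of EoT and the last dose plus 28 or 14 days would add a new error. With a single dose on D155, D114 to D154 (41 days without a dose) would become treatment-emergent. This rules out that remedy, but not a separate tabulation.
- **Sources not shown.** The sponsor's safety-reporting standard cited in 4.3.5, or the protocol, may deal with rescue. That is possible, but the SAP's own definition assigns all of follow-up to post-TEAE without exception.

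**Conclusion.** The point holds as a gap in classification and presentation. Events that start after follow-up dupilumab are moved to the post-TEAE category and pooled with events in undosed children, so no planned table shows on-drug incidence in follow-up. The TEAE and AESI incidence tables are affected for certain once such an event occurs. The PCSA counts are affected only if the combined period wording means the TEAE period for patients.

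The size cannot be computed, because the SAP does not give the number of children who receive follow-up dupilumab. If none do, nothing changes. With about 24 patients, each child with such an event is 1/24 = 4.2 percentage points, and two are 8.3. The 43% is a per-child upper bound on time; it must not be read as an estimate of bias in any reported percentage.

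The conclusion rests on two assumptions: that at least one child is dosed in follow-up, and that no document outside the SAP already separates these events.

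**What to change.** 1. Keep the TEAE period to EoT as written, so the Week 16 tables are unchanged.
2. State in 4.3.2.4 whether dupilumab given in follow-up counts as study drug, and reconcile the TEAE, exposure and concomitant-medication windows accordingly. If it counts, say how the undosed gap after Week 16 is treated, because last dose minus first dose includes it. If it does not, limit the last dose in both rules to the treatment phase and drop the 156–197 day category.
3. In the final analysis, split the summary of post-TEAE events into two columns: onset from the first follow-up dupilumab dose to the last such dose plus 28 or 14 days (the SAP's own medication window), and all other post-TEAE events. Do the same for AESIs and PCSAs, and give the number of children dosed in follow-up as the denominator of the first column.
4. In 4.3.5.2, say which period applies to patients and which to healthy volunteers.

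The cost is a few sentences and one extra column, probably with small counts. No new data are needed if follow-up dupilumab doses are recorded with dates.

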4.3.5.2 Vital signs

Heart rate, systolic and diastolic blood pressures (SBP and DBP), body temperature and respiratory rate will be analyzed as raw parameter value and change from baseline.

Body weight will be analyzed as raw parameter value and percent change from baseline. BMI will be analyzed as raw parameter value.

Baseline definition

The values to be used as baseline will be the Day 1 (Visit 2, Week 0) predose assessment. If any of the scheduled baseline tests are repeated for any participant, the last rechecked values will be considered as baseline, provided, for patients, they were done before the IMP administration of the respective treatment phase, and in the same condition.

Abnormalities analyses

For vital sign parameters, analysis will be performed using all post-baseline assessments done during the TEAE period/safety period, including all unplanned and rechecked values. Counts of participants with potentially clinically significant abnormal (PCSA) values will be presented by cohort, regardless of the baseline status. PCSA values are defined as abnormal values considered medically important by the Sponsor according to predefined criteria/thresholds based on literature review and defined by the Sponsor.

A listing of individual data from participants with post-baseline PCSAs will be provided; values will be flagged when reaching the PCSA criteria.

PCSA criteria are detailed in [Section 8 \(Appendix D\)](#).

Descriptive statistics and plots

For heart rate, blood pressures, body temperature and respiratory rate, raw data and absolute changes from baseline will be summarized in descriptive statistics for patients' cohort and scheduled time of measurement.

For body weight, raw data and percent change from baseline will be summarized in descriptive statistics by cohort and scheduled time of measurement.

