8.4 APPENDIX D POTENTIALLY CLINICALLY SIGNIFICANT ABNORMALITIES (PCSA) CRITERIA

Table 3 - PCSA criteria for vital signs parameters for studies in children (24 May 2014)

CRITERIA for POTENTIALLY CLINICALLY SIGNIFICANT ABNORMALITIES For Studies in Children			
Parameter	Age range	PCSA	Comments
Vital Signs			Ref. : Kidney Disease Outcomes Quality Initiatives (KDOQI) Guideline 13; 1996; The fourth report on the diagnosis, evaluation, and treatment of high blood pressure in children and adolescents, Pediatrics 2004; Bowman E & Fraser S Neonatal Handbook 2012; Mulberg AE et al. Pediatric Drug Development Concepts and applications. John Wiley & sons, Inc. 2009; Pediatric respiratory rates http://www.health.ny.gov/
SBP	6 to <12 years old (Children)	≤ 80 mmHg and decrease from baseline ≥ 20 mmHg ≥ 108 mmHg and increase from baseline ≥ 20 mmHg	Based on definition of Hypertension as average SBP or DBP $\geq 95^{\text{th}}$ percentile for gender, age, and height on ≥ 3 occasions
	12 to 16/18 years old (Adolescents)	≤ 90 mmHg and decrease from baseline ≥ 20 mmHg ≥ 119 mmHg and increase from baseline ≥ 20 mmHg	
DBP	6 to <12 years old (Children)	≤ 48 mmHg and decrease from baseline ≥ 10 mmHg ≥ 72 mmHg and increase from baseline ≥ 10 mmHg	
	12 to 16/18 years old (Adolescents)	≤ 54 mmHg and decrease from baseline ≥ 10 mmHg ≥ 78 mmHg and increase from baseline ≥ 10 mmHg	
Temperature	All age ranges	Rectal, ear or temporal artery: ≥ 100.4 °F/38.0 °C Oral or pacifier: ≥ 99.5 °F/37.5 °C Axillary or skin infrared: ≥ 99 °F/37.2 °C	Ear temperature not accurate below 6 months of age
Respiratory rate	6 to <12 years old (Children)	<18 per minutes >30 per minutes	Based on normal range
	12 to 16/18 years old (Adolescents)	<12 per minutes >20 per minutes	
Weight	All ranges	≥ 5 % weight loss from baseline	Based on identification of trends in the child's growth with a series of visits WHO Multicentre Reference Study Group, 2006; Center for Disease Control. Growth chart 2007

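### Respiratory-rate and temperature PCSA counts ignore baseline status, so the summary table cannot separate a pre-existing abnormality from a new one

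*SAP*

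**What the plan says.** SAP 4.3.5.2, under Abnormalities analyses, sets the data and the counting rule. The "analysis will be performed using all post-baseline assessments done during the TEAE period/safety period, including all unplanned and rechecked values". Then: "Counts of participants with potentially clinically significant abnormal (PCSA) values will be presented by cohort, regardless of the baseline status". The same subsection plans a listing of participants with post-baseline PCSAs, with the values flagged.

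Appendix D, Table 3, has two kinds of criteria:

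- **Limit plus change, or change alone.** The lower systolic criterion at 6 to <12 years is "≤ 80 mmHg and decrease from baseline ≥ 20 mmHg". The other blood-pressure criteria are built the same way, and weight is a percentage loss from baseline.
- **Limit alone.** Respiratory rate at 6 to <12 years is "<18 per minutes >30 per minutes", and at 12 to 16/18 years "<12 per minutes >20 per minutes". Temperature is a single upper limit for each measuring route.

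Raw values and absolute changes from baseline for respiratory rate and temperature are summarised for the patients' cohort only, whereas the PCSA counts are presented for both cohorts.

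**The concern.** Ignoring baseline status does little harm where the criterion itself contains a change from baseline. A child with a stable low systolic pressure cannot meet the systolic criterion. Respiratory rate and temperature have no such protection, so the count mixes two different things: children who crossed the limit after baseline, and children who were already beyond it and stayed there.

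The PCSA count is the only planned summary count of abnormal vital signs. With about 24 patients, one child is 1/24 = 4.2 percentage points. A reader comparing the cohorts, or looking for a signal in patients, cannot tell from the table how much of a count was present before dosing.

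A second, smaller matter is the age row. Patients enter below 12 years ("The treatment will be given to the pediatric patient (≥ 6 and < 12 years of age) depending on its body weight"), the respiratory limits change at 12, and 4.3.5.2 does not say which age selects the row.

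**Working it through.** **The plan's own figure.** The SAP gives no expected PCSA count. Its only sample-size figure reproduces: 20/(1 − 0.15) = 23.5, rounded up to 24. The 24 is used below only as a denominator.

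**Step 1: does the rule count an unchanged child?** Take an 8-year-old with a rate of 16 at Day 1 and at every later visit. Since 16 < 18, each reading is a PCSA under the 6 to <12 row. Baseline status is disregarded, so the child is counted. This step needs no assumption beyond the text. A child with a stable systolic pressure of 78 mmHg meets the absolute part (≤ 80) but has a change of 0, not ≥ 20, and is not counted.

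**Step 2: how many could this be?** The documents give no distribution of respiratory rate, so two are assumed:

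- *A:* 18 to 30 is a central 95% range, so mean = (18 + 30)/2 = 24 and SD = 6/1.96 = 3.06.
- *B:* mean 20, SD 3.

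Both use Normal values, one baseline and five post-baseline readings, equal within-child correlation ρ of 0.5 or 0.8, no drug effect, and 400,000 simulated children. *Flagged* means at least one post-baseline reading below 18 or above 30. *Pre-existing* means flagged and also outside the limits at baseline. Results are per 24 children; the last column rounds each reading to a whole breath.

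| Scenario | ρ | Flagged | Share already outside at baseline | Pre-existing | Pre-existing, whole-number rates |
|---|---|---|---|---|---|
| A | 0.5 | 4.4 | 14% | 0.6 | 0.4 |
| A | 0.8 | 3.1 | 30% | 0.9 | 0.6 |
| B | 0.5 | 13.7 | 38% | 5.2 | 4.0 |
| B | 0.8 | 10.6 | 53% | 5.6 | 4.4 |

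Pre-existing is flagged × share, for example 4.4 × 0.14 = 0.6 and 13.7 × 0.38 = 5.2. The range is thus about 0.4 to 0.9 of 24 under A and about 4 to 6 of 24 under B.

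The remaining flagged children (70 to 86% under A, 47 to 62% under B) were inside the limits at baseline. They crossed later by chance, because several readings are each compared with a fixed limit.

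**Step 3: the age row.** Classifying whole-number rates under both respiratory rows:

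- 18 to 20: normal in both rows.
- 21 to 30: normal below 12 years, PCSA from 12.
- 12 to 17: PCSA below 12 years, normal from 12.

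For patients the treatment-emergent period is "defined as the time from the first IMP administration up to the EoT visit (EoT included"), that is Day 1 to Day 113, or 112 days. If entry ages are uniform over the six years from 6 to <12 (assumed), the share turning 12 in that time is 112/365.25/6 = 5.1%, and 24 × 0.051 = 1.2 children. This counts birthdays, not misclassified children. A row switch also needs the row to follow age at the assessment, and it alters a count only if a rate in an affected range is recorded after the birthday.

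**The case against.** **The rule is disclosed.** The SAP says openly that baseline status is disregarded, does not call these counts treatment-emergent, and predefines no hypothesis test (5.6). This stands: nothing is contradicted. A reader might infer that the plan presents pre-existing values as drug effects, and the text does not support that. The point is only that the table cannot separate the two.

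**Other outputs cover it.** The flagged listing, the change-from-baseline summaries and the presentation of baseline with later safety values (4.3.2.3) let a reader find a stable abnormal child. This stands in part. The listing works case by case, and the change summaries for these two parameters omit healthy volunteers, so the by-cohort count remains unsplit.

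**The age-12 route may not exist.** A reader might infer that a steady rate of 21 to 30 becomes a PCSA on the twelfth birthday. The SAP does not establish this. Table 3 is a general paediatric table, so its adolescent row may be template text. Age at each visit is specified only for the EASI multipliers (4.1.4). The sponsor's safety-reporting document cited in 4.3.5 may settle the rule. If age is fixed at Day 1, no child under 12 at entry changes row. What is left is a missing statement.

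**The size is easily overstated.** It would be wrong to read the 3.1 to 4.4 of 24 flagged under A, or the 10 to 14 under B, as pre-existing abnormalities, since these totals include chance crossings. B also rests wholly on an assumed mean and SD. Five readings is an assumption too: Appendix C schedules only two post-baseline vital-sign checks for healthy volunteers (Weeks 8 and 16), so fewer would be flagged there. All of this stands.

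**Conclusion.** The concern holds for respiratory rate and temperature, and not for blood pressure or weight. As written, 4.3.5.2 counts a child whose respiratory rate or temperature was already beyond the limit before dosing and did not change, and the summary table cannot distinguish that child from a new case. This follows from the text alone.

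Its size is not known from the documents. For respiratory rate it is a fraction of one child in 24 if the child limits span a central 95% range, and about 4 to 6 in 24 if typical rates lie near the lower limit (mean 20, SD 3). Both depend on the assumed distribution, five readings and correlation 0.5 to 0.8. Temperature was not quantified.

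The choice of age row is an unresolved ambiguity and a secondary matter. The whole point is minor: it concerns a descriptive safety table and does not touch the TEWL endpoints.

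**What to change.** In 4.3.5.2:

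1. Keep the overall PCSA count. For respiratory rate and temperature, add counts by cohort in two columns: children without that PCSA at baseline (missing baseline included here) and children with the same PCSA at baseline. For respiratory rate, judge low and high separately.
2. State whether age on Day 1 or age at the assessment selects the Appendix D row, or cite the sponsor document that says so. The split needs this too, because otherwise a child's baseline and later readings could be judged by different rows. Either choice has a consequence to note: under Day 1 age, a rate of 12 to 17 recorded after the twelfth birthday is still flagged; under age at the assessment, a steady 21 to 30 becomes flagged.

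The cost is two sentences and one split of an existing table, with no new data and no change to any threshold. The downside is small cells, especially in the column for children already PCSA at baseline. The split separates pre-existing values only. It does not remove chance crossings from repeated readings, which stay in the other column, so a table footnote giving the number of post-baseline readings per child in each cohort would help the reader.
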